2.8 Safety

Safety analyses include adverse events (AEs), serious adverse events (SAEs) and Hb-related safety endpoints. Additional safety presentations are described below ([Section 7](#) and [Section 10](#)).

3 Analysis Populations

3.1 The Analysis Populations

The following analysis populations are used in this trial:

- Randomized population: defined as all subjects randomized. Analyses of this population will be based on the randomized treatment.
- Full Analysis Set (FAS) population: defined as all subjects in the randomized population who received at least 1 dose of study medication and had at least 1 post dose Hb. Analyses of this population will be based on the randomized treatment.
- Per protocol (PP) population: defined as all randomized subjects who received study medication during the primary evaluation period, had at least 1 Hb assessments during the primary evaluation period, and had no critical or major protocol deviation affecting the primary endpoint analyses (ie, prior to Week 26). Analyses of this population will be based on actual treatment received, as described for the Safety population.
- Safety population: defined as all subjects in the randomized population who received at least 1 dose of study treatment. Analysis of this population will be based on the actual treatment received. Subjects who received in error some vadadustat and some

darbepoetin alfa (excluding rescue therapy) will be classified by the more frequently received drug.

- Pharmacokinetic (PK) population: defined as all subjects in the safety population who have at least 1 measurable vadadustat plasma concentration.

Efficacy analyses will utilize the randomized, FAS, and PP populations while safety analyses will utilize the safety population. PK analyses will utilize the PK population.

3.2 Characterization of the Analysis Population

Number and percent of subjects included in the analysis sets will be summarized.

4 Quality of the Trials

4.1 Study Drug Dosing and Compliance

The IMP (vadadustat or darbepoetin alfa) dosing electronic case report forms (eCRFs) will collect study drug dosing information and whether they have experienced any problems related to the dosing of IMP.

The study drug compliance rate for a given time period will be derived from exposure data as the number of days on dosing period collected on eCRFs divided by the number of days in that time period.

The average weekly dosages and the proportion of subjects who have at least 80% compliance will be tabulated and summarized by treatment group and analysis period for safety and FAS populations. The number and percentage of subjects with any study medication interruptions and their reasons for interruption, collected in eCRF, will be summarized as well.

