## **6.4 Subject Compliance**

Subjects will be questioned regarding dosing compliance at every visit and whether they have questions or have experienced any problems related to the dosing of the IMP (vadadustat or darbepoetin alfa). Treatment compliance will be determined from drug accountability logs along with the subject questioning and the IMP eCRFs. Dosing compliance for vadadustat or darbepoetin alfa is defined as 80% to 120% over the course of the Treatment Period.

Subjects who miss doses will be counseled on the importance of compliance.

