### **End of Treatment Visit/Early Termination Visit**

The EOT Visit will be conducted on Week 52 for subjects that complete the 52-week treatment period ( $\pm$  3 days). For subjects that end treatment prior to Week 52, the ET assessments should be performed within 7 days after stopping IMP.

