2.2 Study Periods

Following randomization, the study has 2 study periods during the trial:

- **Conversion and Maintenance Treatment Period (Weeks 0 to 52):**
 - Weeks 0 to 20: conversion to investigational medicinal product (IMP) for maintaining hemoglobin (Hb).
 - Weeks 20 to 26: primary efficacy period (PEP).
 - Weeks 26 to 46: ongoing maintenance period.
 - Weeks 46 to 52: secondary efficacy period (SEP).

- **Safety Follow-up Period (Early Termination [ET] and Follow-up):** post-treatment Safety Follow-up Visit (ET/End of Treatment [EOT] + 4 weeks).

Individual subjects will participate in total trial duration of approximately 64 weeks. An exit interview will also be conducted at the EOT visit at a subset of sites. Subjects' end of study (EOS) will be their safety follow-up visit (ET/EOT+4 weeks) or if afterwards, the date of the determined survival status per documented attempt(s) as defined in the protocol.

The analysis time periods for efficacy divide the Conversion and Maintenance Treatment period into five windows (see [Table 1](#)).

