4.3 Baseline Characteristics, Exposure, and Retention by Treatment Group

Descriptive statistics will be generated by treatment group for demographic and pretreatment variables for each analysis population.

The total number of randomized subjects, treated subjects, and randomized but not treated subjects will be tabulated by treatment group in the randomized population.

The number of subjects who discontinued the study and the reason for discontinuation will be summarized for randomized population.

Medical history terms will be coded using the Medical Dictionary for Regulatory Activities (MedDRA) and summarized by system organ class (SOC) and preferred term (PT) for each treatment group based on the safety population.

5 General Conventions

Study days are defined as follows:

Study Day = [Event date – First dosing date + 1] if on or after first dosing date
[Event date – First dosing date] if before first dosing date.

Note that with the definition above, days of “0” will not be used. As such, the study day can be interpreted as the number of days before or after first day of dosing. Event date refers to the date associated with the result being summarized. In some cases, this is the date of an assessment or measurement; in other cases, this is the onset date of an adverse or outcome event.

For subjects whose reference date is missing, the study day will also be categorized as missing.

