5.1 Visit and Analysis Time Period Classification

The time windows in this section reflect the administrative range around each visit for analysis. They are wider than those stated in the protocol to reduce missing values by capturing as many observation dates as possible. [Table 1](#). provides the convention to classify assessment dates into protocol-defined visits and analysis time periods for assessments conducted at every visit, such as Hb value.

Unless otherwise specified, all assessments will be mapped to visit windows based on the date of the assessment relative to the first dose date, regardless of subject disposition or the CRF page completed, e.g., “Unscheduled”, “End of Treatment”, etc. Similarly, all values collected within a reporting period will be considered for identification of safety events of interest.

If more than 1 Hb value is available in an analysis time period post-baseline, the average of all observed values (at most 1 per day) will be assigned to that period. For example, the

window for the primary efficacy outcome, analysis time period 3, includes any Hb value (at most 1 per day) assessed between Study Days 127 to 196, corresponding to Weeks 20, 24 and 26.

Efficacy evaluations will use Hb values as assessed by the central laboratory.

When more than 1 assessment is made for other measures (not Hb) within a given visit window post-baseline, the value of the assessment closest to the end of the window is the value associated with that visit for summaries over time. Most summaries of results by visit (e.g., laboratory or vital sign results) will use the single value for each visit determined by this convention. Notable exceptions to this convention are the primary efficacy outcome and clinically significant changes.

If no assessment is available within a time window, then the associated visit and week classifications will be missing.

Table 1. Classification of Assessments at Every Visit

Time Period	Visit/Week	Target Day	Actual Study Day of Visit
Baseline	Screening Visit 1	-	-
	Screening Visit 2	-	-
	Baseline Visit	Day 1	Day 1 (first dose date) ^a
1) Weeks 2-8	Week 2	Day 14	Day 2-21
	Week 4	Day 28	Day 22-35
	Week 6	Day 42	Day 36-49
	Week 8	Day 56	Day 50-63
2) Weeks 10-16	Week 10	Day 70	Day 64-77
	Week 12	Day 84	Day 78-98
	Week 16	Day 112	Day 99-126
3) Primary Efficacy Period (PEP) (Weeks 20-26)	Week 20	Day 140	Day 127-154
	Week 24	Day 168	Day 155-175
	Week 26	Day 182	Day 176-196
4) Weeks 30-42	Week 30	Day 210	Day 197-224

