14.1.9.2.2	Study Treatment Compliance Rate by Visit	Full Analysis Set Population
14.1.9.3.1	Average Weekly Dose of Study Treatment	Safety Population
14.1.9.3.2	Average Weekly Dose of Study Treatment	Full Analysis Set Population
14.1.9.3.3.1	Average Weekly Dose of Study Treatment by Baseline Hb Category	Safety Population
14.1.9.3.3.2	Average Weekly Dose of Study Treatment by Baseline ESA Type	Safety Population
14.1.9.3.3.3	Average Weekly Dose of Study Treatment by Baseline ESA Dose Group	Safety Population
14.1.9.4.1	Number of Subjects by Vadadustat Dose Level	Safety Population
14.1.9.4.2	Number of Subjects by Vadadustat Dose Level	Full Analysis Set Population
14.1.9.5.1	Summary of Maximum Increase in Dose Amount of Darbepoetin Alfa	Safety Population
14.1.9.5.2	Summary of Maximum Increase in Dose Amount of Darbepoetin Alfa	Full Analysis Set Population
14.1.9.6.1	Total Duration of Exposure (Week) to Study Treatment During the Study	Safety Population

Table Number	Table Title	Population
14.1.9.6.2	Total Duration of Exposure (Week) to Study Treatment During the Study	Full Analysis Set Population
14.1.9.7.1	Reason for Study Drug Change and Interruption	Safety Population
14.1.9.7.2	Reason for Study Drug Change and Interruption	Full Analysis Set Population
14.2.1.1	Change from Baseline in Hemoglobin (Hb, g/dL) to the Average over Weeks 20-26 (ANCOVA with Multiple Imputations)	Randomized Population
14.2.1.2.1	Change from Baseline in Hemoglobin (Hb, g/dL) to the Average over Weeks 20-26 (ANCOVA with Multiple Imputations)	Full Analysis Set Population
14.2.1.2.2	Change from Baseline in Hemoglobin (Hb, g/dL) to the Average over Weeks 20-26 (ANCOVA with Multiple Imputations)	Per Protocol Population
14.2.1.2.3.1	Change from Baseline in Hemoglobin (Hb, g/dL) to the Average over Weeks 20-26 (ANCOVA with Multiple Imputations of Data Affected by any Rescue - Narrow Therapy with $\geq 50\%$ Increases in Darbepoetin Alfa Treatment)	Randomized Population
14.2.1.2.3.2	Change from Baseline in Hemoglobin (Hb, g/dL) to the Average over Weeks 20-26 (ANCOVA with Multiple Imputations of Data Affected by any Rescue - Narrow Therapy with $\geq 100\%$ Increases in Darbepoetin Alfa Treatment)	Randomized Population
14.2.1.2.4.1	Change from Baseline in Hemoglobin (Hb, g/dL) to the Average over Weeks 20-26 (ANCOVA with Multiple Imputations of Data Affected by any Rescue - Broad-on-treatment Therapy with $\geq 50\%$ Increases in Darbepoetin Alfa Treatment)	Randomized Population

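### The SAP 4.1 compliance denominator runs past the end of treatment in the last analysis period, so a fully dosed completer scores only 75.7% to 84.3% against an 80% cut

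*SAP*

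**What the plan says.** SAP 4.1 derives compliance from exposure data as "the number of days on dosing period collected on eCRFs divided by the number of days in that time period". It then says that "the proportion of subjects who have at least 80% compliance will be tabulated and summarized by treatment group and analysis period", for the safety and FAS populations. It gives no rule for ending the denominator at the last dose or at the EOT visit.

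SAP 2.2 says that the analysis time periods for efficacy "divide the Conversion and Maintenance Treatment period into five windows" and points to Table 1. In Table 1 (SAP 5.1) period 5, the secondary efficacy period, runs from Day 309 to Day 378. The Week 52 visit has target Day 364 and window Days 358-378. Of these windows SAP 5.1 says: "They are wider than those stated in the protocol to reduce missing values by capturing as many observation dates as possible". Days are counted from first dose: "Study Day = [Event date – First dosing date + 1] if on or after first dosing date".

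Protocol section 8 fixes the end of treatment: "The EOT Visit will be conducted on Week 52 for subjects that complete the 52-week treatment period", with a tolerance of ± 3 days. SAP 19 lists compliance tables by study period (14.1.9.1.1 and 14.1.9.1.2) and also "Study Treatment Compliance Rate by Visit" (14.1.9.2.1 and 14.1.9.2.2). Protocol 6.4 takes a different basis: compliance "is defined as 80% to 120% over the course of the Treatment Period".

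**The concern.** The Table 1 windows were widened so that late blood draws could be assigned to a visit. That is sensible for haemoglobin. It does not suit a count of dosing days, because the last window extends about two weeks beyond the point at which treatment is planned to stop. Table 1 shows this itself: safety follow-up starts 15 days after EOT, so for an EOT on Day 364 the whole of Days 365-378 is post-treatment and yet still lies in period 5.

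A ratio with those days in its denominator cannot reach 100% for an on-schedule completer, however good the adherence. The reporting cut of 80% happens to fall inside the range of best attainable scores. The compliance table for Weeks 46-52 would then sort perfectly adherent subjects by visit date. The same rule charges a subject who stops early for the rest of the window in which treatment stopped, so discontinuation is reported as non-compliance. Protocol 9.3 expects up to 30% of subjects to discontinue.

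**Working it through.** The plan states no compliance figure to reproduce, so the check is a direct count.

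**Inputs**
- Period 5: Days 309-378, so 378 − 309 + 1 = 70 days (SAP Table 1).
- Week 52 window: Days 358-378, so 378 − 358 + 1 = 21 days (SAP Table 1).
- EOT: Day 364 ± 3, so Days 361 to 367 (SAP Table 1 target day; Protocol section 8 and Trial Duration).
- Day 1 is the first dose date (SAP 5).
- Assumption: the eCRF dosing period of a fully adherent subject runs without a gap to the last dosing day, L.

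**Formulas**
- Period 5 rate = (L − 308) / 70
- Week 52 by-visit rate = (L − 357) / 21
- Days that cannot hold a dose = 378 − L, which is 17, 14 and 11 days for L = 361, 364 and 367

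| Last dosing day | Period 5 | Week 52 window |
|---|---|---|
| 361 | 53/70 = 75.7% | 4/21 = 19.0% |
| 362 | 54/70 = 77.1% | 5/21 = 23.8% |
| 363 | 55/70 = 78.6% | 6/21 = 28.6% |
| 364 | 56/70 = 80.0% | 7/21 = 33.3% |
| 365 | 57/70 = 81.4% | 8/21 = 38.1% |
| 366 | 58/70 = 82.9% | 9/21 = 42.9% |
| 367 | 59/70 = 84.3% | 10/21 = 47.6% |

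A subject who finishes exactly on Day 364 passes with nothing to spare. One day earlier fails.

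**Share of fully dosed completers below 80% in period 5.** The documents do not give the distribution of the last dosing day, so this can only be a range:
- uniform over Days 361-367 (last dose on the visit day): 3/7 = 43%
- uniform over Days 360-366 (last dose the day before): 4/7 = 57%
- uniform over Days 362-368 (Week 52 counted as Day 365): 2/7 = 29%
- everyone on Day 364: 0%; everyone on Day 363: 100%

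**Other windows.** Periods 1 to 4 end on Days 63, 126, 196 and 308, all within treatment for a completer, so completers are affected only in period 5. Subjects who discontinue can be affected in any window. For example, daily dosing from Day 309 with a last dose on Day 343 gives 35/70 = 50%.

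**After the fix.** With the denominator ended at L, the completer finishing on Day 364 scores 56/56 = 100% and the discontinuer above scores 35/35 = 100%.

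**The case against.** The strongest reply is that SAP 4.1 never cites Table 1. Table 1 exists to classify assessment dates, and dosing days are not assessments. SAP 2.2 describes the secondary efficacy period as Weeks 46 to 52, the planned table is titled by study period, and Protocol 6.4 works over the whole treatment period. On a nominal Weeks 46-52 denominator (Days 322-364, 43 days) the same completers score 40/43 = 93.0% to 100%. Over 364 days they score at least 361/364 = 99.2%. Nobody falls below 80% on either basis.

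This shows that another reading is possible, but the text favours the full window. SAP 4.1 uses the term analysis period, and Table 1 holds the only day ranges for those periods. SAP 6.4 already applies the same five periods, with a reference to Section 5.1, to darbepoetin alfa dose increases, so they are not reserved for assessments. For the by-visit table Table 1 is the SAP's only source of day ranges. The Protocol 6.4 basis is no safe fallback either, because SAP 1 says the SAP prevails where the two differ.

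Other parts of the reply do stand:
- A reader might infer that about half of adherent completers will fail the cut. The documents do not support a single figure, since the share depends entirely on an unstated last-dose distribution.
- A reader might infer that every completer fails at Week 52 in the by-visit table. The rates there would be low, but SAP 4.1 specifies the 80% cut by analysis period only, so there is no threshold to fail.
- A reader might infer that the Weeks 46-52 noninferiority result is undermined. Compliance enters neither the analysis model nor the testing sequence, and the per-protocol definition in SAP 3.1 has no 80% criterion.

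**Conclusion.** The point holds as a defect in a stated descriptive rule. Taking SAP 4.1 with Table 1 as written, the best attainable period 5 compliance for an on-schedule completer is 75.7% to 84.3%, set by the EOT date, and the best Week 52 by-visit rate is 19% to 48%. This rests on two things: that the denominator is the full Table 1 window, which is the most natural reading but is not spelled out, and that last dosing falls within Days 361-367.

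The proportion pushed below 80% is 29% to 57% under the three uniform assumptions and could lie anywhere from 0% to 100%. It should not be quoted as a finding. If average weekly dose by period uses the same 70-day divisor, which SAP 4.1 does not say, a Day 364 finisher's period 5 weekly dose would be understated by 14/70 = 20%.

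The consequence is confined to the compliance tables, and possibly the weekly dose tables. A reader of the study report could take a calendar effect for poor adherence. No estimate, test or analysis population changes.

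**What to change.** In SAP 4.1, state the following:
- Each denominator ends at the earlier of the window end and the subject's last IMP dose, with EOT taken as the end for completers.
- A subject whose last dose precedes the start of a window is left out of that window. Without this, a subject whose last dose was on Day 200 would have a period 5 denominator ending before it begins.
- Discontinuation is reported separately and not through the compliance rate.
- Average weekly dose by period uses the same divisor.

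The cost is a short addition to the SAP text and a programming change, with no new data. There is one small downside: days after early discontinuation no longer count as non-compliance, so a subject who stops early can score 100% in the last window that counts. The compliance tables must therefore be read with the disposition table, and a footnote should say so.

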4.2 Protocol Deviations

Protocol deviations will be summarized in the randomized population as the number and percentage of subjects with a protocol deviation by treatment group. A by-subject listing of protocol deviations will be provided. Protocol deviations due to coronavirus disease 2019 (COVID-19) will be summarized as well.

4.3 Baseline Characteristics, Exposure, and Retention by Treatment Group

Descriptive statistics will be generated by treatment group for demographic and pretreatment variables for each analysis population.

The total number of randomized subjects, treated subjects, and randomized but not treated subjects will be tabulated by treatment group in the randomized population.

The number of subjects who discontinued the study and the reason for discontinuation will be summarized for randomized population.

Medical history terms will be coded using the Medical Dictionary for Regulatory Activities (MedDRA) and summarized by system organ class (SOC) and preferred term (PT) for each treatment group based on the safety population.

5 General Conventions

Study days are defined as follows:

Study Day = [Event date – First dosing date + 1] if on or after first dosing date
[Event date – First dosing date] if before first dosing date.

Note that with the definition above, days of “0” will not be used. As such, the study day can be interpreted as the number of days before or after first day of dosing. Event date refers to the date associated with the result being summarized. In some cases, this is the date of an assessment or measurement; in other cases, this is the onset date of an adverse or outcome event.

For subjects whose reference date is missing, the study day will also be categorized as missing.

5.1 Visit and Analysis Time Period Classification

The time windows in this section reflect the administrative range around each visit for analysis. They are wider than those stated in the protocol to reduce missing values by capturing as many observation dates as possible. [Table 1](#). provides the convention to classify assessment dates into protocol-defined visits and analysis time periods for assessments conducted at every visit, such as Hb value.

Unless otherwise specified, all assessments will be mapped to visit windows based on the date of the assessment relative to the first dose date, regardless of subject disposition or the CRF page completed, e.g., “Unscheduled”, “End of Treatment”, etc. Similarly, all values collected within a reporting period will be considered for identification of safety events of interest.

If more than 1 Hb value is available in an analysis time period post-baseline, the average of all observed values (at most 1 per day) will be assigned to that period. For example, the

window for the primary efficacy outcome, analysis time period 3, includes any Hb value (at most 1 per day) assessed between Study Days 127 to 196, corresponding to Weeks 20, 24 and 26.

Efficacy evaluations will use Hb values as assessed by the central laboratory.

When more than 1 assessment is made for other measures (not Hb) within a given visit window post-baseline, the value of the assessment closest to the end of the window is the value associated with that visit for summaries over time. Most summaries of results by visit (e.g., laboratory or vital sign results) will use the single value for each visit determined by this convention. Notable exceptions to this convention are the primary efficacy outcome and clinically significant changes.

If no assessment is available within a time window, then the associated visit and week classifications will be missing.

Table 1. Classification of Assessments at Every Visit

Time Period	Visit/Week	Target Day	Actual Study Day of Visit
Baseline	Screening Visit 1	-	-
	Screening Visit 2	-	-
	Baseline Visit	Day 1	Day 1 (first dose date) ^a
1) Weeks 2-8	Week 2	Day 14	Day 2-21
	Week 4	Day 28	Day 22-35
	Week 6	Day 42	Day 36-49
	Week 8	Day 56	Day 50-63
2) Weeks 10-16	Week 10	Day 70	Day 64-77
	Week 12	Day 84	Day 78-98
	Week 16	Day 112	Day 99-126
3) Primary Efficacy Period (PEP) (Weeks 20-26)	Week 20	Day 140	Day 127-154
	Week 24	Day 168	Day 155-175
	Week 26	Day 182	Day 176-196
4) Weeks 30-42	Week 30	Day 210	Day 197-224
	Week 34	Day 238	Day 225-252
	Week 38	Day 266	Day 253-280
	Week 42	Day 294	Day 281-308
5) Secondary Efficacy Period (SEP) (Weeks 46-52)	Week 46	Day 322	Day 309-336
	Week 50	Day 350	Day 337-357
	Week 52	Day 364	Day 358-378
Safety Follow-up	Follow-up	ET/EOT + 4 Weeks	ET/EOT+15 Days – ET/EOT+42 Days

ET=Early Termination; EOT=End of Treatment.

^a If patient has no first dose date, day 1 will be the randomization date.

